3.1.3 Clinical Benefit Rate

Clinical benefit rate (CBR) is a secondary endpoint in Parts 1 and 2.

CBR is defined as the number (%) of patients with an AML IWG best response of CR, CRi or partial remission (PR). Data obtained up until progression, or last evaluable assessment in the absence of progression, will be included in the assessment of CBR. This will be irrespective of whether or not patients discontinued treatment or received a subsequent therapy prior to progression.

All efficacy data collected, whether based on scheduled or unscheduled visits, will be included in the assessment of CBR, with the exception of data collected following the start of subsequent AML therapy, which will not be included in the assessment of OCRR.

In all study parts, the primary analysis of CBR will be assessed based on the evaluable for response (EFR) set with a sensitivity analysis based on the full analysis set (FAS).

3.1.4 BM Blasts

The percentage change from baseline in BM blasts at Day 29 is a secondary endpoint in all study parts and will be evaluated for the EFR set (primary) and FAS (sensitivity).

3.1.5 Time to Response

Time to response (TTR) will be derived as the time from first dose to first response (CR, CRi or PR). As described in Section 3.1, if the peripheral blood and bone marrow assessments for a visit are performed on different dates, TTR will be calculated using the date of the bone marrow assessments.

3.1.6 Time to CR

Time to CR (TTCR) will be derived as the time from first dose to first CR or CRi. As described in Section 3.1, if the peripheral blood and bone marrow assessments for a visit are performed on different dates, TTCR will be calculated using the date of the bone marrow assessments.

3.2 Safety and Tolerability

3.2.1 Safety Endpoints

The assessment of safety and tolerability is a co-primary objective of Part 1, and a secondary endpoint of Part 2. In both study parts, the safety and tolerability of ASLAN003, in AML patients, will be assessed using the following endpoints:

- Adverse Events (AEs)
- Physical Examination
- Vital Signs (blood pressure [systolic and diastolic], heart rate, respiration rate, and body temperature)
- Laboratory assessments (clinical chemistry, hematology, coagulation and urinalysis)
- 12-lead Electrocardiogram (ECG) (P and QRS duration, RR, PQ, QT and QTc intervals using Bazett's and Fridericia's formulae)
- Treatment exposure and dose intensity

In addition, tolerability will be further explored by assessment of dose reductions, interruptions and modifications (see Section 3.2.2).

Adverse events will be coded by System Organ Class (SOC) and Preferred Term (PT) using the Medical Dictionary for Regulatory Activities (MedDRA) for concomitant diseases and AEs and World Health Organization (WHO) Drug for medications. All AEs will be evaluated for severity according to NCI-CTCAE version 4.03

Baseline will be defined as the last assessment prior to the start of study treatment. If multiple assessments are performed at the same pre-treatment timepoint, for example triplicate ECG assessments, the mean of the values will be used as the baseline reading.

Creatinine clearance will be derived as:

$$eC_{Cr} = \frac{(140 - Age) \times Mass \text{ (in kilograms)} \times Constant}{Serum Creatinine \text{ (in } \mu\text{mol/L)}}$$

where constant=1.23 for males and 1.04 for females, and will be categorized as 30-
<60 ml/min, 60-<90 ml/min and =>90 ml/min. Creatinine clearance will be included in summaries of the clinical chemistry data.

QTcB will be derived as:

$$QTcB = \frac{QT}{\sqrt{RR}}$$

QTcF will be derived as:

$$QTcF = \frac{QT}{\sqrt[3]{RR}}$$

For derivation of post-baseline visit values, taking account of possible visit windows, see Section 3.2.1.1.

3.2.1.1 General Considerations for Safety Assessments

Missing safety data will not be imputed. However, safety assessment values of the form of “< x” (i.e., below the lower limit of quantification) or “> x” (i.e., above the upper limit of quantification) will be imputed as “x” in the calculation of summary statistics but displayed as “< x” or “> x” in the listings.

In order to produce data summaries by visit, visit time windows are required, and will be derived using the following conventions:

- The time windows will be exhaustive so that data recorded at any time point has the potential to be summarized. Inclusion within the time window should be based on the actual date and not the intended date of the visit.
- All unscheduled visit data should have the potential to be included in the summaries.
- The window for the visits following baseline will be constructed in such a way that the upper limit of the interval falls half way between the two visits (the lower limit of the first post-baseline visit will be Day 1). If an even number of days exists between two consecutive visits then the upper limit will be taken as the midpoint value minus 1 day.

Furthermore, the following principles will apply to the presentation of safety data:

- For summaries showing the maximum or minimum values, the maximum/minimum value recorded on treatment will be used (regardless of where it falls in an interval).
- For summaries of the ECG data, the mean value of the triplicate readings will be included in the summaries.
- Listings should display all values contributing to a time point for a patient.
- For visit based summaries:
 - If there is more than one value per patient within a time window then the closest value should be summarized, or the earlier in the event the values are equidistant from the nominal visit date. The listings should highlight the value for that patient that went into the summary table, wherever feasible.
 - To prevent very large tables or plots being produced that contain many cells with sparse data, for each treatment group, visit data should only be summarized if the number of observations is greater than 1/3 of patients dosed.
- For summaries at a patient level, all values should be included, regardless of whether they appear in a corresponding visit based summary, when deriving a patient level statistic such as a maximum.
- Baseline will be defined as the last non-missing measurement prior to dosing with study treatment. For laboratory data, any assessments made on day 1 will be considered pre-dose unless explicitly indicated otherwise. Where safety data are summarized over time, study day will be calculated in relation to date of first treatment (which will be termed day 1).
- Study Day will be calculated from the reference start date, and will be used to show start/ stop day of assessments and events.

Reference start date is defined as the day of the first dose of study drug, (Day 1 is the day of the first dose of study drug), and will appear in every listing except medical history where an assessment date or event date appears.

- If the date of the event is on or after the reference date then:
 - Study Day = (date of event – reference date) + 1
- If the date of the event is prior to the reference date then:
 - Study Day = (date of event – reference date)

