7.2.2.6 Cycle 2 and Subsequent Cycles - Day 1 (± 2 days)

On Day 1 of Cycle 2 and all subsequent cycles, the following procedures will be conducted:

- Complete physical examination;
- Body weight;
- Vital signs (blood pressure, heart rate, respiratory rate, body temperature);
- 12-lead ECG (only on Cycle 2 Day 1);
- All AEs since the last visit will be recorded;

- Concomitant medications will be recorded;
- Routine laboratory evaluations (chemistry, hematology, liver function test and urinalysis);
- Study drug (ASLAN003) will be dispensed and administered.
- BM aspiration is mandatory to be performed on Day 1 of every cycle from Cycle 2 to Cycle 5 and every 3 months thereafter. Patients achieving CR could omit the bone marrow aspiration at a subsequent assessment if there is a normal complete blood count with differential of peripheral blood. Investigator may perform additional BM aspirate if required based on clinical judgment. BM aspiration smear will be processed locally.

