7.2.4 Safety Follow-up (± 7 days)

Patient will complete a safety follow-up visit 28 days after the last dose of ASLAN003. The following procedures will be performed:

- Complete physical examination;
- 12-lead ECG
- Vital signs (blood pressure, heart rate, respiratory rate, body temperature);
- All AEs since the last visit will be recorded;
- Concomitant medications will be recorded.

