8.4.3.3 Vital Signs and ECG measurements

Vitals signs and ECG data will be listed. In addition, all data measured on a continuous scale (except respiration rate and pulse) will be displayed graphically as described below:

- Patient profile plots to show both absolute values, and the % change from baseline over time. For Part 1, separate plots will be produced for each dose cohort.
- Box plots of the change from baseline over time, by dose cohort (Part 1 ONLY), including a horizontal reference line at zero.

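### The SAP's visit windows have no last-dose cut, so End-of-Treatment and 28-day follow-up ECG and vital-sign values enter the by-visit box plots as treatment-visit values

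*SAP*

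**What the plan says.** SAP 3.2.1.1 sets the rule for by-visit safety summaries. Coverage is total: "The time windows will be exhaustive so that data recorded at any time point has the potential to be summarized". Placement ignores the visit label: "Inclusion within the time window should be based on the actual date and not the intended date of the visit". For boundaries, "the upper limit of the interval falls half way between the two visits", with a one-day adjustment when the number of days is even. On duplicates, "If there is more than one value per patient within a time window then the closest value should be summarized". A visit is shown only if its observations exceed one third of patients dosed. Study day is counted from the first dose.

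The section has one on-treatment limit, for extremes: "the maximum/minimum value recorded on treatment will be used". SAP 7.7.1 also uses on-treatment maxima in the liver scatter plots. By-visit summaries have no such limit.

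Two visits are timed from the last dose instead of the first. Protocol 7.2.3 places EOT within 7 days of it. Protocol 7.2.4 says: "Patient will complete a safety follow-up visit 28 days after the last dose of ASLAN003", with a ±7 day window. Both collect ECG and vital signs. After baseline, the only scheduled on-treatment ECGs are Cycle 1 Day 15 and Cycle 2 Day 1, which is Day 29 (Protocol Table 1).

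The output that pools these values by visit is described in Protocol 8.4.3.3 as "Box plots of the change from baseline over time, by dose cohort (Part 1 ONLY), including a horizontal reference line at zero". SAP 7.7.1 plans the same, and SAP 9.3 lists them as Figures 14.3.5.3 and 14.3.6.3.

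**The concern.** EOT and Safety Follow-up have no nominal study day, so the midpoint rule cannot build slots for them and the SAP gives them none. Exhaustive windows by actual date then send their values to the nearest treatment visit. A box labelled Cycle 2 Day 1 can contain readings from patients who stopped weeks earlier, and the figure gives no sign of it.

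Safety and tolerability is a co-primary basis for choosing the dose in Part 1, and a cohort has six patients, so a few misplaced values are a large share of a box. If stopping differs by dose, so does the mix of on-drug and off-drug values. Early stopping is plausible: in the earlier study of healthy elderly subjects at 100 mg QD, five were dosed on Day 1 and one completed 14 days (Protocol 1.4). The misplaced values also count towards the one-third display rule.

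**Working it through.** The plan states no figure to reproduce. The check applies the SAP rule to the protocol's visit schedule.

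**Windows.** An even number of days can mean the difference between nominal days (reading A) or the days strictly between them (reading B). I assume each assessment's windows are built from its own scheduled visits; the SAP does not say. Example: ECG visits at Days 15 and 29 have midpoint 22. The difference, 14, is even, so A ends the first slot at Day 21. The days between, 13, are odd, so B ends it at Day 22.

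| Assessment | Nominal day | Slot, reading A | Slot, reading B |
|---|---|---|---|
| ECG | 15 | 1–21 | 1–22 |
| ECG | 29 | 22 onward | 23 onward |
| Vital signs | 8 | 1–11 | 1–10 |
| Vital signs | 15 | 12–18 | 11–17 |
| Vital signs | 22 | 19–25 | 18–24 |
| Vital signs | 29 | 26–42 | 25–43 |
| Vital signs | 57 | 43–70 | 44–71 |

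Vital-sign slots then repeat every 28 days.

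**Placement.** With EOT at +7 and follow-up at +28 days, both readings agree:

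- Last dose Day 10: EOT is Day 17 (Day 15 slot) and follow-up is Day 38 (Day 29 slot), for ECG and vital signs.
- Last dose Day 20: EOT is Day 27 (Day 29 slot, both measures). Follow-up is Day 48, so its vital signs go to the Day 57 slot.
- Last dose Day 84: follow-up is Day 112, so its vital signs go to the Day 113 slot. Because 28 days is one cycle, this recurs for late stoppers.
- A patient who reaches Day 29 keeps the true Day 29 ECG, through the closest-value rule.

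**How often.** Take every last dose from Day 1 to 28, EOT at +0 to +7 and follow-up at +21 to +35: 28 × 8 × 15 = 3,360 combinations. An EOT or follow-up ECG fills the Day 29 slot in 100% (A) or 99.8% (B). Follow-up fills it in 63% (A) or 66% (B), and EOT in 38% or 34%. One or two vital-sign slots are filled this way in every combination. These are shares of timing combinations, not probabilities, and they assume that both visits take place. A patient with only an early EOT may leave the Day 29 slot empty.

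**On or off drug.** The half-life is 16 h (Protocol 1.4, healthy subjects). Follow-up: 28 × 24 / 16 = 42 half-lives, and 21 × 24 / 16 = 31.5 at the earliest. If the half-life were three times as long (assumption), 28 × 24 / 48 = 14. EOT varies: the fraction remaining is 0.5^(24/16) = 35% at 1 day and 0.5^(168/16) = 0.07% at 7 days. An EOT on the last dosing day is not off drug.

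**Illustrative size.** Assume every on-drug change is 10 units and fully reverses. If m of n values are off drug, the mean is 10 × (1 − m/n).

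| Values in slot | Mean | Median |
|---|---|---|
| 1 of 6 off drug | 8.3 | 10 |
| 2 of 6 off drug | 6.7 | 10 |
| 3 of 6 off drug | 5.0 | 5 |
| 2 of 3 off drug | 3.3 | 0 |

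The median of a box plot therefore moves less regularly than the mean, while the box widens.

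**Display rule.** More than one third means at least 3 of 6 in a Part 1 cohort and at least 7 of 20 in Part 2. One on-drug plus two off-drug values passes in a cohort of six.

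**The case against.** The strongest reply accepts the placement and disputes the consequence.

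- The pooled outputs are descriptive box plots. Respiration rate and pulse are excluded, which leaves blood pressure, temperature and ECG. Profile plots show each patient's own line, listings show every contributing value, and SAP 9.1 lists no ECG or vital-sign summary table. This stands and limits the reach.
- The liver is the risk singled out for monitoring (Protocol 1.4 and 1.5). No laboratory tests are scheduled at Safety Follow-up, and the liver scatter plots use on-treatment maxima. This stands; laboratory box plots share only the EOT part of the problem.
- Stopping is visible elsewhere: discontinuations due to adverse events, exposure, dose intensity and swimmer plots. Dose selection reviews the data as a whole. This stands too.
- Some off-drug values are intended, because Protocol 3.4 keeps scheduled assessments during interruptions. That is true, but it does not cover visits after a permanent stop.
- The display-rule example is contrived for the Day 29 ECG, where most early stoppers would supply a value. It is more plausible for later vital-sign slots.

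A reader might infer more: that a dose causing more stopping will look cleaner, with its ECG or vital-sign change understated by a third or a half. The documents do not support that. They give no effect size and do not show that any effect reverses after stopping. Progression, infection or new therapy could move later values either way. The 33% and 50% figures are reductions of a mean under assumed full reversal, not of a box-plot median.

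**Conclusion.** The point holds as a labelling fault with limited reach. As written, the SAP places EOT and Safety Follow-up values in treatment-visit slots, and no other section prevents it. Follow-up values are off drug; EOT values may or may not be. The Day 29 ECG slot is the clearest case, given windows built from the ECG schedule and both visits completed.

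The effect is mainly on the by-visit box plots of change from baseline in ECG, blood pressure and temperature, and on the one-third display rule. Values shown as treatment-visit values are not all on-treatment values. If drug effects reverse, they dilute the on-drug change; otherwise the direction is open. Nothing here shows that the dose decision would be wrong. The rule merits correction because it departs from the on-treatment limits the SAP already applies to extremes and the liver plots.

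**What to change.** Amend SAP 3.2.1.1 to state three things:

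1. Only values up to the day after the last dose, including scheduled visits during temporary interruptions, are assigned to nominal treatment visits and counted for the one-third rule.
2. Values collected as EOT or Safety Follow-up are always summarised in their own slots, timed from the last dose.
3. All values stay in the listings.

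The cost is one SAP rule and a last-dose condition in the windowing program. No data are lost, and the separate follow-up slot shows what happens after stopping.

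The downside is fewer values at later visits, some of which may fall below the one-third rule. Later slots will describe only patients still under treatment, so selective dropout remains. Those plots should be read with the discontinuation and exposure summaries.

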7.2.2.2 Cycle 1, Day 8 (± 1 day)

The following procedures will be conducted at this visit:

- Complete physical examination;
- Vital signs (blood pressure, heart rate, respiratory rate, body temperature);
- All AEs since the last visit will be recorded;
- Concomitant medications will be recorded;
- Routine laboratory evaluations (chemistry, hematology, liver function test and urinalysis);
- Study drug (ASLAN003) will be dispensed and administered.

- Blood sample will be collected for PK analysis at Day 8, QD regime: pre-dose, 1, 2, 4, 5, 6, 8, and 24 hours post dose. In BID regime i.e 100mg BID and 200mg BID the PK sampling will be done at following timepoints: pre-dose, 1, 2, 4, 5, 6, 8, and 12 hours (or evening pre-dose). For Part 2- Steering Committee will decide whether PK analysis is required or not and ASLAN pharmaceuticals will be updated accordingly.

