7.2.2.3 Cycle 1, Day 10 (+1 day)

The following procedures will be conducted at this visit:

- AST, ALT and total bilirubin to be performed;
- Study drug (ASLAN003) will be dispensed and administered.

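### The SAP's visit windows count a protocol-compliant Day 8 liver test held on Day 9 as Day 10, so one valid value drops out of the by-visit displays

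*SAP*

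**What the plan says.** SAP 3.2.1.1 assigns each safety value to a window by the date it was taken, not by the visit it was meant for. A window's upper limit lies half way to the next visit, with one adjustment: "If an even number of days exists between two consecutive visits then the upper limit will be taken as the midpoint value minus 1 day". The windows are defined for visits after baseline ("The window for the visits following baseline will be constructed in such a way"), yet the same rule starts the first of them on Day 1: "the lower limit of the first post-baseline visit will be Day 1). If an even number of days exists between two consecutive visits". Where a patient has several values in one window, "then the closest value should be summarized, or the earlier in the event the values are equidistant from the nominal visit date". On baseline, the section takes the last non-missing value before dosing and states: "For laboratory data, any assessments made on day 1 will be considered pre-dose unless explicitly indicated otherwise". Missing safety data are not imputed.

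Protocol Table 1 and sections 7.2.2.2 and 7.2.2.3 schedule full chemistry on Cycle 1 Day 8 with an allowance of one day either side. They add a Day 10 visit, with an allowance of one day later only, for liver tests alone: "AST, ALT and total bilirubin to be performed". Footnote c to Table 1 lets a screening test from the week before dosing replace the Day 1 test.

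The outputs that use the windows are the by-visit laboratory summaries (Protocol 8.4.3.2) and the box plots of change from baseline over time (SAP 7.7.1; Figure 14.3.4.7 in SAP 9.3).

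**The concern.** Days 8 and 10 are only two days apart, so the one-day subtraction for even gaps matters here. It hands Day 9 to the Day 10 window, although Day 9 is a permitted date for the Day 8 visit and not for the Day 10 visit. Two genuine liver results then compete for one slot and one is discarded, while the Day 8 slot loses its value.

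A second looseness sits in the same sentence. Day 1 is the first day of the first post-baseline window and also the day whose laboratory values count as baseline. No sentence expressly removes the baseline record from that window, so two programmers could fill the vacated Day 8 slot differently.

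Liver-test elevation is the effect the protocol singles out for monitoring (Protocol 1.4 and 1.5). Safety is a co-primary endpoint of Part 1, and each cohort has only 6 patients.

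**Working it through.** The documents give no numeric window limits, so there is no stated figure to reproduce. The limits follow from the rule.

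**Inputs.** Nominal days for AST, ALT and total bilirubin after baseline: 8, 10, 15, 22, 29, then every 28 days (Protocol Table 1). Allowances: ±1 day at Day 8, +1 at Day 10, ±2 afterwards. Window rule and choice rule: SAP 3.2.1.1.

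**Formula.** For consecutive visits on days a and b, the midpoint is (a + b)/2. If b − a is even, upper limit = midpoint − 1. If b − a is odd, the midpoint is a half-day and the last whole day before it is the limit.

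| Visit | Next | Gap | Midpoint | Upper limit | Window | Compliant dates | Outside own window |
|---|---|---|---|---|---|---|---|
| 8 | 10 | 2 (even) | 9 | 8 | 1–8 | 7–9 | **9** |
| 10 | 15 | 5 | 12.5 | 12 | 9–12 | 10–11 | none |
| 15 | 22 | 7 | 18.5 | 18 | 13–18 | 13–17 | none |
| 22 | 29 | 7 | 25.5 | 25 | 19–25 | 20–24 | none |
| 29 | 57 | 28 (even) | 43 | 42 | 26–42 | 27–31 | none |
| 57 | 85 | 28 (even) | 71 | 70 | 43–70 | 55–59 | none |

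Day 9 is the only compliant date up to the Day 57 visit that misses its own window.

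**The other reading of the even-number condition.** If it counts only the days strictly between visits, Days 8 and 10 have one day between them (odd), the limit is 9 and Day 9 stays with Day 8. But the odd gaps in the table then become the even cases, and the limits are 12.5 − 1 = 11.5, 18.5 − 1 = 17.5 and 25.5 − 1 = 24.5. A rule that subtracts a whole day and still leaves half-days is not usable as written, so the gap reading is the coherent one.

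**A patient whose Day 8 visit is on Day 9**, with no other test on Days 2 to 8:

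- Day 10 test on Day 10: distances from Day 10 are 1 and 0. The Day 10 value is shown and the Day 9 value drops out.
- Day 10 test on Day 11: distances are 1 and 1, a tie. The earlier value (Day 9) is shown as Day 10 and the Day 11 value drops out.
- No Day 10 test: the Day 9 value is shown as Day 10.
- In all three cases the Day 8 cell is empty if the Day 1 value is treated as baseline. If the window is programmed by date alone, the Day 1 value fills it, with a change of zero.

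**Other laboratory tests.** If windows are built per parameter, a test not scheduled on Day 10 goes from Day 8 to Day 15: midpoint 11.5, window Days 1 to 11, and Day 9 is placed correctly. The misplacement then concerns only the three liver tests.

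**How often.** One of the three permitted Day 8 dates is affected. The documents do not say how many patients would be seen on Day 9. If p is the assumed probability of a Day 9 visit, the chance that at least one of 6 patients is moved is 1 − (1 − p)^6: 91% for p = 1/3, 74% for p = 1/5 and 47% for p = 1/10. One patient is 1/6 = 17% of a cohort.

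**The case against.** Three arguments weigh against the point.

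First, Day 9 is equidistant from Days 8 and 10, and the SAP deliberately assigns by actual date, so any rule must put it somewhere. That is fair, but the protocol's allowances break the tie: Day 9 is compliant for the Day 8 visit and cannot be compliant for a Day 10 visit that may only run late. The rule resolves the tie the wrong way.

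Second, the affected output is narrow. The SAP's table list (9.1) contains no by-visit chemistry table, although Protocol 8.4.3.2 promises summaries by visit; the liver display that is listed and uses the windows is the box plot. On-treatment maxima ignore the windows, the ALT and AST plots against bilirubin use those maxima, and profile plots and listings keep every value. The dose decision rests on the totality of the data (Protocol 6.1 and 8.4.2). All of this stands, and it sets the severity.

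Third, a reader might infer that the pre-dose Day 1 value becomes the patient's Day 8 result, so that early liver rises are understated. On an even spread over Days 7 to 9, 2 of 6 patients would carry a zero, and the displayed mean change would be 4/6 of the true mean, 33% too low (assuming the same mean change in both groups). The documents do not support that as the expected result. The windows are for visits after baseline and Day 1 laboratory values are baseline, so the natural reading leaves the cell missing and unimputed. A missing cell shrinks the denominator but adds no zeros. A Day 1 test may not exist at all, since screening can stand in for it. The 33% holds only under date-only programming with a Day 1 test present.

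**Conclusion.** Minor, but wrong as written rather than merely under-specified. On the only workable reading of the even-gap rule, a compliant Day 9 liver test is labelled Day 10. When the Day 10 test is also done, one of the two results is lost from the by-visit summaries and change-from-baseline box plots. The Day 8 cell is normally empty; a false zero appears only if the Day 1 lower limit is programmed without regard to the baseline definition.

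The direction and size of the distortion cannot be fixed from the documents. They depend on how many patients are seen on Day 9, how fast enzymes are changing between Days 8 and 11, and how the baseline record is handled. The 91%, 74% and 47% figures describe the chance that some patient in a cohort of 6 is moved, under assumed rates; they say nothing about understatement. Nor is it shown that the Part 1 dose choice would change, because the outputs most relevant to liver injury do not use the windows.

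**What to change.** In SAP 3.2.1.1:

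1. Start the first post-baseline window on Day 2, or state that the baseline record is excluded from every post-baseline window.
2. For AST, ALT and total bilirubin, state the Cycle 1 windows explicitly: Day 8 = Days 2 to 9 and Day 10 = Days 10 to 12. The Day 15 window stays at Days 13 to 18.

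Check: Days 7 to 9 lie in 2–9, Days 10 to 11 in 10–12 and Days 13 to 17 in 13–18. Every compliant date in the table above then falls in its own window, and no Day 1 value can appear as Day 8.

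The cost is about two lines of SAP text and the matching programming. No new data are needed.
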